The clinical study described in this protocol is a safety and efficacy study in order to develop a non-hybrid, fully automated closed loop system that does not require the person to announce meals to the system, and which utilizes the hormone analog pramlintide in combination with insulin to potentially reduce the meal related hyperglycemia and increase the time spent in target range during the daytime.

Primary Objectives:

- To evaluate safety and efficacy of a fixed co-ratio insulin and pramlintide delivery strategy under closed loop control after a meal is detected by the meal detection algorithm
- To evaluate performance of the fully closed-loop system with (1) insulin+pramlintide as compared to (2) insulin-only as measured by incremental area under the curve (iAUC) in the 6 hours following the first meal period

Secondary Objective:

- To evaluate performance of the fully closed-loop system with insulin+pramlintide as compared to insulin-only for other glycemic outcomes

Study Hypothesis:

Our hypothesis is that pramlintide and insulin delivered after a meal by a closed loop system in response to automated meal detection will be well tolerated and will allow for a reduction in the postprandial glucose response as measured by the incremental area under the CGM curve (iAUC) compared with an insulin-only fully closed loop system.

Endpoints***Primary Endpoints:***

- Incremental area under the curve (iAUC) of postprandial glucose as measured by CGM in the 6 hours following the start of first meal. iAUC (mg/dL*min) will be calculated using a trapezoidal method [76], which sums all CGM values in the 6 hour period following the meal above the starting glucose.
- Percent of time with sensed glucose between 70 – 180 mg/dl in the 6 hours following the start of first meal.

Secondary Endpoints

- Incremental area under the curve (iAUC) of postprandial glucose as measured by CGM in the 6 hours following the start of second meal. iAUC (mg/dL*min) will be calculated using a trapezoidal method [76], which sums all CGM values in the 6 hour period following the meal above the starting glucose.
-

- Percent of time with sensed glucose between 70 – 180 mg/dl in the 6 hours following the start of second meal.

(The following secondary outcomes will be measured in the 6 hours following (1) the start of the first meal, (2) the start of the second meal, and (3) full study duration):

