- Net area under the curve (netAUC) of postprandial glucose as measured by CGM in the 6 hours following the start of first meal. netAUC (mg/dL*min) will be calculated using a trapezoidal method [76], which sums all CGM values in the 6 hour period following the meal above the starting glucose and subtracts CGM values below the starting glucose.
- Percent of time with sensed glucose <70 mg/dl
- Percent of time with sensed glucose between 70 – 140 mg/dl
- Mean sensed glucose
- Percent of time with sensed glucose <54 mg/dl
- Percent of time with sensed glucose >180 mg/dl
- Percent of time with sensed glucose >250 mg/dl
- Mean amount of insulin delivered (in units and units/kg)
- Mean amount of pramlintide delivered (in mcg and mcg/kg)
- Coefficient of variation
- LBGI
- HBGI
- Safety endpoints (over full study duration):
 - Adverse events
 - Number of adverse events probably or possibly associated with pramlintide administration (see ‘Causality Relationship’ below)
 - Baxter Retching Faces (BARF)/VAS scale for gastrointestinal issues after first and second meal, see Protocol Appendix D.
 - Mean duration of gastrointestinal issues after first and second meal as reported by participant on BARF/VAS scale, see Protocol Appendix D.
 - Episodes of carbohydrate intake to treat hypoglycemia (defined as 15g carbohydrate intake)
 - Episodes of hypoglycemia defined as CGM <70mg/dL for 10 minutes or more
 - Number of provider-administered insulin injections due to hyperglycemia

Study Type

This is a single-center, crossover trial designed to evaluate glucose outcomes of a fully closed-loop system with insulin+pramlintide dosed in response to meal detection as compared to an insulin alone fully closed loop system.

Study Population

Study population will be adults with type 1 diabetes, ages 18 – 70 years of age. Younger participants are excluded as it is appropriate to assess safety first in the over 18 year old population. We are targeting a total of 35 participants to complete the full study protocol.

[figure not shown]
Power Analysis

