A sample size of 35 participants provides 90% power to detect a standardized paired mean difference of 0.56 SD, or 80% power to detect a 0.49-SD difference with a two-sided test at the .05 level of significance. This is calculated using a paired t test to approximate a mixed model with treatment, period, and sequence effects. Data from a previous study [24] showed a 0.64-SD reduction with pramlintide in 4-hour postprandial AUC for participants with >40 U bolus insulin per day. We plan to recruit more than half of our study participants from this population and so we expect to observe a slightly smaller reduction in AUC.

Protocol Summary:

Participants will undergo two study visits to evaluate (1) insulin+pramlintide versus (2) insulin-only delivery strategies. The order of the visits will be randomized. Meal scenarios will be identical across all study arms. Participants will arrive at approximately 7:30 am for all visits, be monitored through the afternoon and discharged at approximately 8 pm. During each study visit, participants will wear Omnipod(s) to deliver insulin and/or pramlintide and a Dexcom G6 CGM to measure glucose and a Polar M600 to measure activity levels. See Figure 1 and 2 below.

Figure 1: Study flow diagram

Time	Activity	Hours post meal
7:30 AM	Begin closed loop study	0
8 AM	Breakfast	1
9 AM		2
10 AM		3
11 AM		4
12 PM		5
1 PM		6
2 PM	Lunch	1
3 PM		2
4 PM		3
5 PM		4
6 PM		5
7 PM		6
8 PM	Discharge	

Figure 2: Treatment visit timeline

Subject Criteria

Inclusion Criteria:

1. Diagnosis of type 1 diabetes mellitus for at least 1 year.
2. Participants 18 to 70 years of age.
3. Current use of an insulin pump for at least 3 months with stable insulin pump settings for >2 weeks. OR Current use of multiple day injection insulin therapy with stable doses for >2 weeks.
4. Uses a carbohydrate ratio, at least occasionally, to dose meal time insulin
5. HbA1c \leq 10.5% at screening.
6. Total daily insulin requirement is less than 139 units/day.
7. Willingness to follow all study procedures, including attending all clinic visits.
8. Willingness to sign informed consent and HIPAA documents.

Exclusion Criteria:

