Participants who will be taking an NPH dose prior to discharge from the clinic and who currently do not use a CGM or are not actively using their personal CGM will continue to use the study CGM for approximately 12 hours after the visit completes. Study staff will complete a phone check-in the next day to remove the CGM. The participants will be asked to check glucose from CGM at 2am the morning after their treatment visit. If the CGM value is above 150 mg/dl, participants will be asked to take 80% of the correction bolus. If the glucose is less than 100 mg/dL they will be instructed to take 15 grams of carbohydrate.

Participants will be given a snack to take with them for the trip home. Participants will also be advised to monitor their glucose for any symptoms of hyperglycemia or hypoglycemia, before

their next meal, and at bedtime. Study staff will call the participant approximately 1 hour after discharge and participant will obtain a fingerstick glucose at that time.

If a study visit is stopped prematurely, such as due to technical problems, the participant will be asked if they can repeat the study visit that was terminated early with additional compensation provided. Repeating the study visit will be optional.

Adverse Events

Causality relationship to Pramlintide administration

The causality of each AE should be assessed by the Investigator according to the following classification:

Probable: Good reason and sufficient documentation to assume a causal relationship.

Possible: A causal relationship is conceivable and cannot be dismissed.

Unlikely: The event is most likely related to etiology other than the pramlintide administration.

Not related: The event occurs before any pramlintide has been started.

Table 1: Schedule of Events

Automated insulin delivery system abbreviated AID

¹ ins/pram visit

	Screening	Active Treatment		End of Treatment
Description of visit procedures	Screening visit	Dexcom CGM insertion visit	1st AID visit	2nd AID visit
Visit Number	1	2	3	4
Visit Window		1-84 days	1-8 days	3-28 days
Informed Consent	X			
Medical history/	X	X	X	X
Focused physical	X			
Eligibility assessment	X			
Download data from participant's existing insulin pump and glucose sensor (if applicable)	X			
Review medications and doses	X	X	X	X
Hypoglycemia awareness survey	X			
Measure BP, pulse, height and weight	X			
Pregnancy Test (Urine)	X	X	X	X
Hemoglobin A1c	X			
Complete Blood Count (CBC)	X			
Comprehensive Metabolic Panel (CMP)	X			

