The closed-loop study will be stopped and the participant's own pump or basal insulin will be resumed under the guidance of the on call study investigator if any of the following occur after the start of the study: the participant requests that the treatment be stopped, participant pregnancy, one episode of diabetic ketoacidosis as defined as symptoms such as polyuria, polydipsia, nausea, or vomiting, serum ketones > 1.5 mmol/L or moderate/large urine ketones, either arterial blood pH < 7.3 or venous pH < 7.24 or serum bicarbonate < 15 , and treatment

provided in a health care facility including in the absence of hospitalization, severe GI symptoms (i.e. to the point of not being able to tolerate food or liquids or one episode of severe hypoglycemia defined as a hypoglycemic event resulting in altered consciousness requiring another person to actively administer carbohydrate, glucagon, or other resuscitative actions.

Entire study stopping rules

Triggers for reporting unanticipated problems are seizure, hospitalization, death or any other occurrence considered serious by the PI and Medical Monitor. If any studies are stopped for severe hypoglycemia or diabetic ketoacidosis, then the entire study will be halted. Severe hypoglycemia is defined as any event that required the assistance of another person to administer carbohydrate, glucagon, or other resuscitative actions. Diabetic ketoacidosis is classified as: symptoms such as polyuria, polydipsia, nausea, or vomiting, serum ketones >1.5 mmol/L or moderate/large urine ketones, either arterial blood pH <7.3 or venous pH <7.24 or serum bicarbonate <15 , and treatment provided in a health care facility. If an event of severe hypoglycemia or diabetic ketoacidosis should occur, the study will be halted and a description of the serious adverse event and a new risk mitigation plan will be submitted to the FDA. The study will only resume once FDA approval is received. In addition, if there is any unexpected event such as death or patient hospitalization, the studies will be stopped until the root cause is evaluated.

Withdrawal Criteria

The participant may withdraw at will at any time or at the discretion of the Investigator.

A participant must be withdrawn if the following applies:

- Hypoglycemia during the treatment period posing a safety problem as judged by the investigator.
- Hyperglycemia during the treatment period posing a safety problem as judged by the investigator.

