- Protocol deviation having influence on efficacy or safety data as judged by the Investigator.
- Substantial and repeated non-compliance with trial procedures.
- Pregnancy. Intention of becoming pregnant.

Description of the MPC algorithms

Our exercise-aware model predictive control (exMPC) algorithm uses a glucoregulatory model to predict glucose outcomes over a predicted horizon (N_p), and mathematically solve for the optimal insulin doses across the control horizon (N_c) to bring the participant to target. The model is updated at each timestep by a Kalman filter, which uses the difference between CGM observations and model predictions to update the physiologic model states. Exercise is represented by heart rate data collected from a wrist-worn fitness watch. Elevated heart rate is represented by increased glucose disposal in the form of increased insulin sensitivity. In summary, a model-predictive controller uses a physiologic model to calculate how much insulin is required to bring someone to glucose target, and these predictions are adapted to the specific

participant using a Kalman filter. The exMPC algorithm has been described previously and has been clinically evaluated in multiple outpatient studies [79-81].

The Meal Detection feature in the algorithm includes a model for missed meal insulin detection and carbohydrate size estimation[2]. The model includes estimations for carbohydrate consumption based glucose patterns to determine if that person has consumed a meal without announcing it to the system. We refer to this algorithm as the Meal Detection algorithm.

Statistical methods

The primary study endpoints are (1) incremental area under the curve (AUC) of glucose in the 6 hours following unannounced meals and (2) percent of time with glucose sensor 70-180 mg/dL.

The hypothesis to be tested is that pramlintide and insulin delivered after a meal by a closed loop system in response to automated meal detection will improve postprandial glucose control over insulin delivered alone in response to automated meal detection.

Incremental AUC (iAUC) of postprandial glucose (mg/dL*min) will be calculated using a trapezoidal method which sums all CGM values in the 6 hour period following the meal above the starting glucose. (M. M. Tai, "A Mathematical Model for the Determination of Total Area Under Glucose Tolerance and Other Metabolic Curves," Diabetes Care, vol. 17, no. 2, p. 152, 1994, doi: 10.2337/diacare.17.2.152.)

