We will estimate the difference between systems using a fixed effect in a standard 2x2 crossover model with a random participant effect. We will also control for sequence (AB or BA) and period (1 or 2), though we do not anticipate statistically significant effects for these parameters.

We anticipate that the primary outcomes will be approximately normally distributed. We will review the appropriateness of this assumption using both goodness-of-fit tests and diagnostic plots, such as quantile-normal plots. If the normality assumption holds, possibly with a transformation of the outcome, we will test the difference between the study arms using a paired t-test. In the case of mild departures from normality or unequal variances at the two time points, we will re-analyze the primary outcome as the difference between the two visits using bootstrapped standard errors, which avoid distributional assumptions. We will use two-sided tests at the 0.05 level of significance.

Missing data: Missing sensed glucose values will be interpolated for up to 30 min segments. Longer periods of missing data will be omitted if they represent <3% of observation time (which will be truncated if a participant leaves the study early). If the missing data are >3% of observation time, we will use available CBG values to interpolate or impute using measurements. In the case that >2 participants fail to complete the study, we will analyze the primary outcome under multiple imputation using baseline values.

Confidentiality and Protection of Human Subjects

RISKS and BENEFITS

Risks: The risks of the protocol procedures are considered minor. Nonetheless, since pumps and sensors used within automated glucose control systems are imperfect, there is a risk for hyperglycemia and hypoglycemia. All studies will have frequent glucose and ketone samplings and a member of the study staff will be present for studies with a study investigator on call at all times.

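### Observation time is cut at early exit while iAUC is a cumulative 6-hour area, so on the natural reading a visit ended within 6 hours of breakfast scores equal to or better than its full-window value

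*Combined protocol and SAP*

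**What the plan says.** The Endpoints section makes iAUC after the first meal one of two primary endpoints. It is expressed in mg/dL*min and computed by a trapezoidal method that "sums all CGM values in the 6 hour period following the meal above the starting glucose". Statistical methods repeats this definition. Neither place divides by the time observed. The other primary endpoint is the percentage of time at 70–180 mg/dL over the same 6 hours.

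The missing-data paragraph interpolates gaps of up to 30 minutes. Longer gaps are omitted if they stay under 3% of "observation time (which will be truncated if a participant leaves the study early". Above 3%, capillary values are used to interpolate or impute. Multiple imputation, on baseline values, is planned only if more than 2 participants fail to complete.

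The individual stopping rules include "severe GI symptoms (i.e. to the point of not being able to tolerate food or liquids", together with participant request, pregnancy, ketoacidosis and severe hypoglycaemia. Withdrawal Criteria add hypo- or hyperglycaemia judged unsafe, and "Protocol deviation having influence on efficacy or safety data as judged by the Investigator". After a premature stop, with technical problems given as the example, "the participant will be asked if they can repeat the study visit that was terminated early with additional compensation provided"; the repeat is optional. No section says how a partial 6-hour window is scored, which attempt is analysed after a repeat, or what happens to data already collected from a withdrawn participant.

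**The concern.** A cumulative area and a shortened observation period do not fit together. The part of the excursion after exit adds nothing to the sum. Because the denominator ends at exit, the lost hours are also invisible to the 3% rule. With one or two such participants, nothing else in the plan recovers them.

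Early exits are unlikely to be random. The Risks section expects nausea and, more rarely, vomiting with pramlintide, and says it can make hypoglycaemia after a meal more likely. If exits within 6 hours of breakfast are more common at the pramlintide visit, the iAUC comparison tilts towards pramlintide. If exits for hyperglycaemia are more common at the insulin-only visit, it tilts the other way. In both cases a primary endpoint would partly reflect when the visit ended, and the scoring choice could be made after the data are seen.

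**Working it through.** **Inputs from the documents.** Study Population: "We are targeting a total of 35 participants to complete the full study protocol". Power Analysis: this number "provides 90% power to detect a standardized paired mean difference of 0.56 SD, or 80% power to detect a 0.49-SD difference". The calculation there uses a paired t test, two-sided, with alpha 0.05. The documents give no mean, SD or curve for iAUC, so those inputs below are assumptions.

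**1. The plan's own figure.** Paired t test, 34 df, noncentrality d × √35.
- d = 0.56: noncentrality 3.31, power 89.6%.
- d = 0.49: noncentrality 2.90, power 80.4%.

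Both stated figures reproduce.

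**2. What the 3% rule sees.** Take an exit at 120 minutes with a complete trace up to then. Against truncated time, missing is 0/120 = 0%. Against the 6-hour window it is 240/360 = 67%.

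**3. Effect on one visit.** The integrand is never negative, so the area to time t cannot exceed the area to 360 minutes. Assume a triangular excursion, up 100 mg/dL at 120 minutes and back to start at 360:
- Full window: ½ × 360 × 100 = 18,000 mg/dL*min.
- Cut at 2 h: ½ × 120 × 100 = 6,000 (33%).
- Cut at 3 h: 6,000 + 60 × (100 + 75)/2 = 11,250 (63%).

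Other assumed curves start at 140 mg/dL and rise by 120. Four peak at 60 to 180 minutes and decay; one reaches a plateau at 90 minutes.

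| Stop | Share of full iAUC accrued |
|---|---|
| 1 h | 6–27% |
| 2 h | 24–60% |
| 3 h | 43–81% |
| 4 h | 62–92% |

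**4. Effect on the treatment contrast.** Shift in SDs of the paired difference = (m/35) × (1 − s) × k. Here m is the number of truncated visits in one arm, s the share accrued, and k the mean iAUC divided by the SD of the paired difference. With m = 2, the most that does not trigger multiple imputation:
- s = 0.50, k = 1: 2/35 × 0.50 × 1 = 0.03 SD.
- s = 0.15, k = 3: 2/35 × 0.85 × 3 = 0.15 SD.

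Relative to the 0.49-SD detectable effect this is about 6–30%. The triangle cut at 2 h gives 2/35 × 12,000 = 686 mg/dL*min, or 0.07 SD if the SD is 10,000.

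**5. False positives.** Null simulation: mean 20,000, SD 10,000, within-participant correlation 0.5, 40,000 runs. With no truncation, false wins for pramlintide are 2.5%. With two truncated pramlintide visits and s from 0.50 down to 0.15, they are 4.6–6.3%.

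**6. Time in range.** On the triangle, with an assumed start of 120 mg/dL, glucose exceeds 180 from 72 to 216 minutes. Full window: (72 + 144)/360 = 60%. Cut at 2 h: 72/120 = 60%. Cut at 3 h: 72/180 = 40%. On the plateau curve, a stop at 1 h raises it from 9.6% to 53.8%. Truncation can therefore flatter or penalise this endpoint.

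**7. Dividing by observed minutes.** On the curves in the table, with stops from 1 to 5 h, the per-minute iAUC is 0.38 to 1.81 times the full-window value. This is not a safe repair.

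**The case against.** The strongest reply is that the truncation clause is a parenthesis defining the denominator of the 3% rule. It does not say that a partial iAUC enters the analysis with zero area after exit. Since the endpoint is defined over 6 hours, a partial window could also be treated as not evaluable. This stands: the scoring is inferred. But dropping such visits would instead select on tolerability, and the plan does not say that either.

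Several further limits also stand.
- Stopping closed-loop control is not the same as leaving the study. The discharge sections keep the sensor on until just before discharge, so some CGM after a stop may exist, though nothing guarantees it to 6 hours.
- Only stops within 6 hours of breakfast reach the primary iAUC. The stop for high capillary glucose before lunch falls at about 6 hours and largely spares it.
- Severe hypoglycaemia or ketoacidosis halts the whole study, so those visits would not pass unnoticed.
- A GI stop needs severe symptoms, and the run-in is meant to lessen them.
- If glucose stays at or below the starting value after exit, no area is lost.

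A reader might infer that the plan rewards pramlintide for intolerance. The documents do not establish this: they give no exit rates by visit, and exits for hyperglycaemia at the insulin-only visit would push the other way. A reader might also infer that repeats and deviation-related withdrawals let results be replaced or discarded according to how the visit went. The repeat provision gives technical problems as its example, and a repeat can itself reduce truncation. The withdrawal text does not say that collected data are removed. These are unstated details, not demonstrated selection.

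**Conclusion.** The concern holds in limited form and should be fixed; confidence is medium. The plan leaves time after exit outside its missing-data rules unless more than 2 participants fail to complete. Even then it names neither the partial trace nor the other visit as imputation inputs, and does not say whether truncated scores are set to missing. For iAUC the consequence on the natural reading is one-directional within a visit: equal or better, never worse. It would be wrong to extend this to both primary endpoints, since time in range can move either way.

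The shift of 0.03–0.15 SD assumes that both truncated visits are pramlintide visits, that 15–50% of the area had accrued, and that mean iAUC is 1 to 3 SDs of the paired difference. It is modest and could be zero or reversed. It matters because it touches a primary endpoint, may be linked to treatment-related exits, and is cheap to settle in advance.

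**What to change.** 1. Remove the truncation clause for the 6-hour endpoints. Define iAUC and time in range over a fixed 0–360 minute window from the start of the meal.
2. Use any CGM recorded after a closed-loop stop, up to 360 minutes. Treat the remaining time after exit as missing.
3. Impute that time at any number of non-completers, from the CGM up to exit, treatment, period and the other visit's outcome.
4. Add a sensitivity analysis that scores time after the stop unfavourably when the stop was for GI symptoms or glucose.
5. Do not replace iAUC by area per observed minute.
6. As a secondary clarification, state which attempt is analysed when a visit is repeated, and that withdrawal does not remove data already collected.

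The cost is revised analysis wording and slightly more programming, with no extra data. The estimate may become slightly less favourable.

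### The multiple-imputation rule for non-completers names only baseline values as predictors, so as written it omits the participant's own observed visit and does not match the crossover model

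*Combined protocol and SAP*

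**What the plan says.** Statistical methods gives the primary estimator: "We will estimate the difference between systems using a fixed effect in a standard 2x2 crossover model with a random participant effect", with adjustment for sequence and period. The next paragraph says that, if normality holds, "we will test the difference between the study arms using a paired t-test". For mild departures from normality or unequal variances it falls back on a bootstrap of the difference between the two visits. Testing is two-sided at 0.05.

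The Missing data paragraph then adds a rule for dropout: "In the case that >2 participants fail to complete the study, we will analyze the primary outcome under multiple imputation using baseline values". This is the whole imputation specification. It does not define baseline values, give the imputation model, or mention treatment, period, sequence or the observed visit. Nor does it say whether the imputed analysis replaces or supplements the crossover model.

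Power Analysis is based on complete pairs: "This is calculated using a paired t test to approximate a mixed model with treatment, period, and sequence effects". Study Population targets 35 completers, and Subject Recruiting gives an enrollment goal of 35.

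**The concern.** In a two-period crossover, the participant's result at the other visit is usually the best available predictor of a missing one. An imputation model built on baseline values alone draws the missing visit as if, given baseline, it were unrelated to the visit that was observed. Each imputed pair then carries too little within-participant correlation. Its difference is too variable, and both the within- and between-imputation parts of the variance grow. The analysis model assumes the opposite, namely a shared participant effect.

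The rule takes effect at three non-completers, 3/35 = 8.6%, and the enrollment goal leaves no allowance for dropout. From that point the primary comparison could be less precise than one with no imputation at all. The random-participant model already named in the plan can use a single observed visit through the likelihood, without a switch of method.

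**Working it through.** **Inputs from the documents.** N = 35; standardized paired differences of 0.56 and 0.49; two-sided 0.05 (Power Analysis, Statistical methods); crossover model with treatment, period, sequence and random participant; imputation triggered by more than 2 non-completers.

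**Assumed, because the documents do not give them.** Between-visit correlation ρ from 0.2 to 0.8; correlation r between baseline and outcome from 0 to 0.6; 3, 5 or 7 second visits missing completely at random; normal outcomes with SD 1.

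**Step 1: the plan's own power.** For a paired t-test the noncentrality is d√N on 34 df.
- d = 0.56: 0.56 × √35 = 3.313, power 89.6% (plan: 90%).
- d = 0.49: 0.49 × √35 = 2.899, power 80.4% (plan: 80%).

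Both stated figures reproduce. With 30 complete pairs, power at 0.56 is about 84%; with 32 it is about 87%.

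**Step 2: variance without imputation.** For complete pairs with period and sequence in the model,

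Var = [2(1 − ρ)/4] × (1/n₁ + 1/n₂).

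With 5 missing (15 + 15 pairs) and ρ = 0.7: 0.15 × (2/15) = 0.0200, SE 0.141. Generalized least squares on all available visits, which is the mixed model at known correlation, gives 0.01957, SE 0.140. Keeping the single visits therefore helps only slightly.

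**Step 3: simulation with 5 of 35 second visits missing.** There were 1,500 trials per setting and 30 imputations, with Rubin's rules and small-sample df. The true effect was 0.56 SD of the difference, which at ρ = 0.7 is 0.56 × √0.6 = 0.434. Monte Carlo error on power is about 1 point. Cells show mean reported SE and power; the last column is the analytic SE from Step 2.

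| ρ | r | Imputation, baseline only | Imputation with other visit | Complete pairs | Mixed model, SE |
|---|---|---|---|---|---|
| 0.7 | 0 | 0.171, 70.8% | 0.144, 82.5% | 0.141, 83.3% | 0.140 |
| 0.7 | 0.4 | 0.164, 74.7% | 0.143, 84.5% | 0.141, 84.9% | 0.140 |
| 0.7 | 0.6 | 0.156, 79.3% | 0.143, 84.3% | 0.142, 84.1% | 0.140 |
| 0.5 | 0.4 | 0.192, 81.7% | 0.183, 83.9% | 0.183, 83.2% | 0.179 |
| 0.5 | 0.6 | 0.183, 85.9% | 0.180, 86.7% | 0.182, 85.5% | 0.179 |

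A separate set of runs at r = 0.3 gave 72% for baseline-only imputation, 85% for complete pairs and 83% with the other visit at ρ = 0.7. At ρ = 0.5 the figures were 80%, 82% and 83%. At ρ = 0.3 there was no loss.

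At ρ = 0.5 with an uninformative baseline (r = 0) the SEs are 0.198 and 0.183. The effect there is 0.56, so the ratios are 2.83 and 3.06. By the normal approximation power is Φ(0.87) = 81% against Φ(1.10) = 86%, a loss of 5 to 6 points.

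At ρ = 0.2 the baseline-only SEs are 0.230, 0.226 and 0.220 for r = 0, 0.4 and 0.6, against 0.231 for complete pairs and 0.224 for the mixed model. The ordering has reversed against complete pairs and, at r = 0.6, against the mixed model too.

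**Step 4: at the trigger itself (3 missing).** At ρ = 0.7 the baseline-only SE is 0.155, 0.150 or 0.145 against 0.137 for complete pairs, which is 6 to 13% larger. At ρ = 0.5 power is 84-86% against 85%, so there is no real loss.

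**Step 5: where the loss comes from.** With ρ = 0.7, r = 0 and 5 missing, the reported SE is 0.171 but the estimates vary with an SD of 0.145 (complete pairs: 0.138). Sampling error rises by about 5% (0.145/0.138), while the reported SE rises by about 21% (0.171/0.141). Bias was negligible in every setting.

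**The case against.** The strongest reply is that the sentence is incomplete rather than wrong. It does not say that baseline values are the sole predictors, and a statistician implementing it could add the other visit and treatment. That is fair: the restriction is inferred from silence. But baseline values are the only predictors named, and someone following the text would have no instruction to add more.

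Two stronger readings are tempting, and the documents do not support them.
- A reader might infer that the observed visit is thrown away. Nothing removes it from the analysis; on the literal reading it is absent only as a predictor in the imputation.
- A reader might infer bias toward no effect. That would arise only if treatment were also left out of the imputation model, and the plan does not say so.

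Other points also stand in part.
- The loss depends on two correlations that the plan does not give, and it vanishes or reverses when ρ is low.
- The error is conservative: an interval that is too wide, not a false positive.
- The rule may seldom bite. Prematurely stopped visits may be repeated, and the primary outcomes cover the six hours after the first meal, so a visit stopped before lunch can still supply them. Failing to complete the study is therefore not the same as lacking a primary outcome.
- Baseline covariates can help if dropout depends on baseline, which is a reason to keep them in a fuller imputation model.
- Dropping imputation does not by itself bring in incomplete pairs, because the paired t-test and the bootstrap of visit differences both need two visits. The fix has to deal with this.

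**Conclusion.** The point holds in a limited form. As written, the imputation rule does not match the within-participant analysis in the same section, and a better method is already in the plan.

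With 5 of 35 second visits missing, the cost against complete pairs is about 5 to 13 percentage points of power at ρ = 0.7. At ρ = 0.5 it is about 2-3 points with a weak baseline, rather more if baseline predicts nothing, and none at r = 0.6. At about 0.3 or below there is no loss. It would be wrong to conclude that baseline-only imputation is always less precise than no imputation.

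These figures assume normal outcomes, second visits missing completely at random, and treatment included in the imputation. They do not cover dropout that depends on first-visit glucose or gastrointestinal effects. The documents give no expected dropout rate, so five missing visits is an illustration and not a forecast.

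**What to change.** In Statistical methods:

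1. Make the stated mixed model (treatment, period, sequence, random participant), fitted by likelihood to all available visits, the primary analysis for both primary endpoints whatever the number of non-completers. Remove the switch at more than 2.
2. State that this model, not the paired t-test, gives the primary test when pairs are incomplete. State also how the bootstrap fallback treats participants with one visit, since it works on visit differences.
3. If multiple imputation is kept, make it a sensitivity analysis. Its model should contain the observed-visit outcome, treatment, period, sequence and baseline values, with baseline values defined.
4. Apply it to missing primary outcomes, not to failure to complete the study. Say how a participant with no treatment visit is handled, since no other-visit outcome exists for that person.

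The cost is SAP wording and slightly more analysis work. The design, sample size and data collection do not change.
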